### **8.3 Measures of Treatment Compliance**

Treatment compliance will be based on attendance and urine drug tests, thrice weekly for 8 weeks. Each participant will be allowed to reschedule one appointment 24 hours or more in advance, to take place within 24 hours of the original appointment. Missed visits will be counted as a positive drug test. We will use the in vitro urine drug testing for rapid, simultaneous detection of MA, amphetamine, cocaine, opioids, and MDMA in urine.

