## 15 STATISTICAL METHODS AND CONSIDERATIONS

Prior to the analysis of the final study data, a detailed Statistical Analysis Plan (SAP) will be written describing all analyses that will be performed. The SAP will contain any modifications to the analysis plan described below.

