### 15.3 Analysis of Primary Endpoint

Using mixed effects linear regression and marginal plots, we will estimate, graph, and compare trajectories of CTRA gene expression between those with methamphetamine use disorder in the contingency management (MA+/HIV+) and non-substance-using control (MA-/HIV+) conditions.

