### 15.6 Multivariate Analysis for Associations Between Endpoints

Associations between MA use, CTRA gene expression, and viral suppression. All models in Aim 1 will adjust for age, race, education, employment, housing, and mRNA encoding markers of major leukocyte subsets (e.g., CD4). We will also assess for confounding by COVID-19 infection detected by immunoassay, liver function, and type of ART prescription. MA use and CTRA. Using a linear mixed effects regression, we will test whether a negative MA urine test is associated with reductions in CTRA contrast scores across four time points—Visits B, 4.2, 8.2, and 12.0. We will use a time (days) by MA urine result interaction term to estimate difference in change in CTRA as

a function of MA test result. CTRA and viral load. Using a mixed effects logistic regression, we will test whether CTRA gene expression is associated with viral suppression (<200c/mL) across three time points—Visits B, 4.2, 8.2, and 12.0. We will include a time (days) by CTRA gene expression interaction term to test this association longitudinally. We will also test whether CTRA and viral load are reciprocally associated using dynamic panel data modeling with maximum likelihood (102-104). This approach will allow us to simultaneously test whether CTRA is associated with viral load at subsequent observations, and account for whether CTRA is affected by prior values of viral load (102-104).

**Associations between psychosocial indicators of substance use severity and CTRA.** Using a linear mixed effects regression, I will test whether the seven domains of the Addiction Severity Index (ASI) is associated with reductions in CTRA contrast scores across four time points—Visits B, 4.2, 8.2, and 12.0. I will use a time (days) by ASI domain score interaction term to estimate change in CTRA as a function of changes in ASI scoring. We will control for age, race, education, and mRNA markers of major leukocyte subsets.

**Indirect associations between MA use, CTRA, and viral suppression.** I will use propensity scores to test the degree to which CTRA mediates the association between MA use and viral suppression (105, 106). The general theory is that we would compute propensity score for CTRA—the probability of having a particular CTRA level—to compare participants who used MA with those who would have had the same value of the CTRA had they used MA.

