## 15.7 Sample Size and Randomization

This study will enroll 55 participants, who will be evaluated for the course of 14 weeks, including screening. Power analysis for this pilot study indicates that a minimum of 135 person-observations will be sufficient to test whether MA use or the psychosocial Addiction Severity Index (ASI) are associated with CTRA gene expression, assuming a medium effect size of 0.15 and power level of .80. Additionally, a logistic model testing whether CTRA is associated with viral suppression would require a minimum of 154 person-observations, assuming a power level of .80, a CTRA standard deviation of 1.44, mean centering of CTRA, and an odds ratio of 1.5. When modeling viral load as a continuous outcome, 135 person-observations is the minimum to test whether CTRA is associated with viral load (c/mL), assuming a medium effect size of 0.15 and power level of .80. These analyses will include 55 participants over four measurements of CTRA, for a total of 220 person-observations (176 person-observations at 80% retention), which is sufficient for these thresholds.

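### The only term Section 15.6 names for change in CTRA, time by urine result, cannot detect a constant fall in CTRA at negative visits, and the urine effect is left open to stable arm differences

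*Combined protocol and SAP*

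**What the plan says.** Section 15.6, repeated in the synopsis under Primary Analysis Plan, first states an association test: "we will test whether a negative MA urine test is associated with reductions in CTRA contrast scores across four time points" (Visits B, 4.2, 8.2 and 12.0). The next sentence names the only coefficient: "We will use a time (days) by MA urine result interaction term to estimate difference in change in CTRA", by test result.

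The psychosocial model in Section 15.6 is built the same way, with a "time (days) by ASI domain score interaction term to estimate change in CTRA as a function of changes in ASI scoring". The viral-suppression model has a time by CTRA interaction.

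On adjustment: "All models in Aim 1 will adjust for age, race, education, employment, housing, and mRNA encoding markers of major leukocyte subsets". Neither arm nor a time origin is mentioned.

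Section 15.3, the primary-endpoint analysis, will "compare trajectories of CTRA gene expression between those with methamphetamine use disorder in the contingency management (MA+/HIV+) and non-substance-using control (MA-/HIV+) conditions". It has no MA-use term. Section 15.7 describes 135 person-observations as "sufficient to test whether MA use or the psychosocial Addiction Severity Index (ASI) are associated with CTRA gene expression", without saying which term is powered.

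Section 3.1 asks whether CTRA and MA use (and viral load) change together, in men with and without MUD. The synopsis objective speaks of differences rather than changes, and Section 4.1 gives the controls a between-group role. Section 15 promises that "a detailed Statistical Analysis Plan (SAP) will be written describing all analyses that will be performed".

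**The concern.** A time-by-exposure interaction gives a difference in trajectories when the exposure is fixed for each person. Here the urine result is measured again at every CTRA visit, so the term answers a narrower question: does the gap between negative and positive results widen or narrow over the study? A participant whose CTRA drops when he stops using, and stays down by the same amount, contributes nothing to it.

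The Addiction Severity Index (ASI) sentence is the clearer misdescription, because it says outright that a time by score term captures the response to changes in score.

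Two wrong reports are possible. An analyst who reads the interaction as the answer could report no difference in change while CTRA tracks abstinence visit by visit. An analyst who uses the main effect without arm and without a within-person split could report tracking when there are only stable differences between people. The pilot is meant to judge CTRA as a non-abstinence endpoint, so either report bears on its purpose.

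**Working it through.** **1. The plan's own figures (Section 15.7).** 55 × 4 = 220 and 0.8 × 220 = 176; both reproduce. The 135 is not determined by the stated inputs, because alpha, number of predictors and tested term are missing. Reading 0.15 as Cohen's f², with alpha 0.05 and independent rows assumed, an omnibus F test at 80% power needs 135 observations for 14 predictors (131 for 13, 139 for 15). A test of one coefficient needs 55. So 135 is consistent with an overall test and is not shown to describe the interaction.

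**2. Does the exposure vary?** Table 3 schedules a urine test and a PBMC draw at each of B, 4.2, 8.2 and 12.0 in both arms. Same-visit entry is therefore the natural reading, but it is an inference.

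**3. Algebra.** Let CTRA = b0 + b1·t + b2·neg(t) + b3·t·neg(t).
- Negative-minus-positive gap at time t: b2 + b3·t. So b3 is the daily drift of the gap, equivalently the difference in slope by result.
- A person positive at t1 and negative at t2 changes by b1·(t2 − t1) + b2 + b3·t2.
- If CTRA is lower by d at every negative visit, b2 = −d and b3 = 0. A noiseless check with a shift of −0.8 returned −0.800 for the urine coefficient and 0.000 for the interaction.
- With b3 in the model, b2 is the gap at t = 0, so its meaning depends on an origin that the plan does not give.
- For a score S with coefficients c2 (score) and c3 (time × score), moving from S1 to S2 changes CTRA by b1·(t2 − t1) + c2·(S2 − S1) + c3·(t2·S2 − t1·S1). A stable response to score change sits in c2, not c3.

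**4. Size.** From the documents: 35 CM, 20 controls, four visits, 80% retention. Assumed: controls always negative; probability of a negative test in CM 10/50/55/45%; ICC 0.5; days 0/32/60/88; random-intercept REML with Wald z tests at 5%; 2,000 trials per scenario; no covariates.

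| Scenario | Time × result | Main effect, centred, no arm | Main effect, centred, with arm | Within-person (participant mean, arm, visit) | Same with arm × visit |
|---|---|---|---|---|---|
| A. CTRA 0.5 SD lower at each negative visit | 5% | 93% | 88% | 83% | 78% |
| B. No urine effect; CM 0.5 SD higher | – | −0.11 SD, 13% | 0.00, 5% | 0.00, 5% | – |
| C1. Gap grows to 0.7 SD by Week 12, controls decline too | 58% | – | – | 51% | 63% |
| C2. As C1, controls flat | 10% | – | – | 69% | 64% |
| D. CM-only 0.5 SD drop after baseline, unrelated to urine | +0.15 per 30 days, 29% | – | – | −0.08 SD, 8% | 0.00, 5% |

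Percentages are rejection rates.
- In A, the main effect with time from day 0 rejects in 64.5%, and the Section 15.3 arm × time term in 9%.
- Within-person power in A is 68% to 96% for ICC 0.3 to 0.7 and 41% for a 0.3 SD effect. If results persist within person it is 70% (ICC 0.5) or 58% (ICC 0.3).
- In B, arm gaps of 0.3 to 0.8 SD give −0.08 to −0.17 SD and 9% to 21% for the unsplit effect. If heavier users also have stably higher CTRA (assumed correlation 0.3), the results are: unsplit −0.21, 27%; with arm −0.09, 8%; within-person −0.01, 5%.
- Score analogue (constant slope 0.3 SD per unit): time × score averages 0.001 and rejects in 5%; the within-person score term rejects in 75%.

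A separate simulation (CM only, 0.8 drop, between- and within-person SD both 1, days 0/35/63/91, 400 trials) gave 0.000 and 4.5% for the interaction, and −0.79 and 91% for the within-person term.

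**5. Information behind the within-person term.** CM observations: 35 × 4 × 0.8 = 112, below 135. Controls help only through the visit effects; dropping them raises the mean SE from 0.172 to 0.181 and lowers power from 83% to 78%.

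**The case against.** **The phrase can be read as correct.** The slope over days is b1 for positive and b1 + b3 for negative results, so b3 is literally a difference in rate of change by result. This stands. A reader might infer that the protocol gives the interaction a false meaning; the wording does not support that. It is ambiguous, and the term cannot see a constant concurrent fall. If the result were fixed per person, the sentence would be right as written.

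**The plan already has an association test.** A reader might also infer that nothing in the plan addresses Section 3.1. That goes too far. The preceding sentence states the urine association, Section 15.7 powers an association with MA use, and the viral-load part has its own model and a dynamic panel model. What is missing is a coefficient designated as the test of concurrent change in CTRA and MA use.

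**The later SAP can settle it.** It can settle time origin and arm. But an SAP that follows Section 15.6 inherits the interaction as the only named term and an adjustment list without arm.

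**Centring time and adding arm does most of the work.** True: 88% in A and 5% in B. The further gain in false-positive control from the split is 8% to 5%, in one scenario with an assumed correlation. The split is mainly a choice of estimand, made because Section 3.1 asks about change.

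**Between-group contrasts belong to the objective.** Also true, given the synopsis wording and Section 4.1, so they should be reported alongside the within-person effect. The interaction also has a use: in C1 it outperforms the base within-person model.

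**Conclusion.** The concern holds in limited form and should be fixed; confidence is moderate. On the natural same-visit reading, the one coefficient that Section 15.6 and the synopsis name measures drift in the negative-positive gap and has no power beyond the test level against a constant fall at negative visits. The unsplit urine effect, adjusted as listed, absorbs stable arm differences: about -0.11 to -0.12 SD and 13% rejection under an assumed 0.5 SD arm gap. The ASI sentence and the time by CTRA term share the construction.

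The algebra depends only on same-visit entry. The sizes depend on assumed effect, ICC, abstinence rates and visit days. The documents do not support the stronger conclusion that the trial cannot answer its question: the urine results and CTRA values needed are already scheduled at the same visits.

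**What to change.** In Section 15.6 and the synopsis:
- Name the within-person urine coefficient (visit result minus the participant's mean over the CTRA visits) as the test of concurrent change for the MA part of Section 3.1. Include participant mean, arm and visit.
- Add arm × visit as a sensitivity analysis, because the base model is slightly biased in scenario D.
- Report the participant-mean and arm contrasts alongside, and reconcile the synopsis objective (differences) with Section 3.1 (changes).
- Keep time × result, with time centred and arm and arm × time included, as a secondary test of drift.
- Describe the ASI/SIP-R and time × CTRA terms in the same way.
- Say how this analysis relates to Section 15.3 and which is primary.
- Section 8.3 says "Missed visits will be counted as a positive drug test". State whether those results enter the participant mean; a missed CTRA visit has no CTRA value, so they could enter only there.

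In Section 15.7, state that the within-person term rests mainly on the 35 CM participants (about 112 observations at 80% retention), so the 135 figure does not describe it.

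The cost is wording, including the sample-size text, and power: about 82–83% against 93% for the centred unsplit effect under the assumed inputs, and 58–70% if ICC is 0.3 or results persist within person. No extra data are needed.

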**PROTOCOL SYNOPSIS**

TITLE	Expression of stress markers in MSM living with HIV receiving contingency management for methamphetamine use disorder (a.k.a. “EXPRESS+”)
SPONSOR	[name], MPH
FUNDING ORGANIZATION	
NUMBER OF SITES	1
RATIONALE	Determining whether a patient is both feeling better and improving physiologically when treating people living with HIV (PLWH) for methamphetamine use disorder requires identification of a clinically significant measure separate from abstinence. This study will to address this challenge by testing a gene expression (mRNA) pattern identified by the field of social genomics, which may provide insight into both psychosocial health and biological processes that impact chronic disease risk in PLWH receiving MUD treatment.
STUDY DESIGN	This is a within-subjects, two-arm clinical trial with 35 HIV-positive MSM receiving contingency management for treatment of methamphetamine use disorder and 20 HIV-positive MSM serving as a non-substance-using healthy control (N=55 total).
PRIMARY OBJECTIVE	To investigate whether differences in CTRA expression (mRNA) coincide with differences in methamphetamine use and viral load over the course of 12 weeks in HIV-positive MSM with and without methamphetamine use disorder.

SECONDARY OBJECTIVES
	
 
• To investigate whether differences in seven psychosocial dimensions of drug addiction (Short Inventory of Problems Revised (SIP-R))—physical, social, intrapersonal, interpersonal, impulse control—are associated with differences in CTRA gene expression.
 
• To conduct an exploratory pilot investigation to determine the degree to which CTRA mediates the association between METH use and viral suppression.
 

NUMBER OF SUBJECTS
	55

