### 3 STUDY OBJECTIVES

#### 3.1 Primary Objective

To investigate whether changes in CTRA gene expression coincide with changes in MA use and viral load over the course of 12 weeks in HIV-positive MSM with and without MUD.

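### The CTRA–viral suppression model enters CTRA undivided, so on its own it cannot show that changes in CTRA coincide with changes in viral control

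*Combined protocol and SAP*

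**What the plan says.** The primary objective is worded in two ways. Section 3.1 asks "whether changes in CTRA gene expression coincide with changes in MA use and viral load"; the Protocol Synopsis asks "whether differences in CTRA expression (mRNA) coincide with differences in methamphetamine use and viral load".

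For the viral part, section 15.6, like the primary analysis plan in the synopsis, specifies a mixed effects logistic regression: "we will test whether CTRA gene expression is associated with viral suppression (<200c/mL" cut-off. It adds: "We will include a time (days) by CTRA gene expression interaction term to test this association longitudinally". On covariates: "All models in Aim 1 will adjust for age, race, education, employment, housing, and mRNA encoding markers of major leukocyte subsets". Study arm is not in that list. Nor is it among the further factors to be checked for confounding (COVID-19 infection, liver function, type of ART).

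Nowhere is CTRA divided into a man's own mean and the visit's departure from it. This model uses no change scores and no conditioning on the man.

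Two other passages bear on the point. Section 15.6 goes on to a dynamic panel model, fitted by maximum likelihood, that relates CTRA to later viral load and allows for the reverse effect. Section 15.7 bases the logistic sample size of 154 person-observations on "a CTRA standard deviation of 1.44, mean centering of CTRA, and an odds ratio of 1.5", without saying which mean is used for centering.

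**The concern.** A time-varying predictor entered whole in a random-intercept model has one coefficient for two questions. Are men with a usually high CTRA less often suppressed? Is a given man less often suppressed when his own CTRA is up? The coefficient answers the second question only if both effects are equal, which the plan neither states nor tests.

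The design makes a between-man contrast likely. The model pools 35 men with methamphetamine use disorder and 20 non-using controls. Section 4.1 recruits the controls to give a reference CTRA level, and section 1.1 says that methamphetamine use impairs adherence and hinders viral suppression. So the plan itself expects the groups to differ on both variables, and without study arm in the model that gap can load on the CTRA coefficient.

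At stake is the reading of the primary objective: a stable difference between men could be reported as CTRA and viral control moving together.

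**Working it through.** **Step 1. The plan's own figure.** Inputs from 15.7: OR 1.5, CTRA SD 1.44, power 0.80. Assumed: two-sided 5%. The usual formula for logistic regression on a continuous predictor is

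n = (1.960 + 0.842)² / [p(1−p) × (ln OR × SD)²].

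Here ln 1.5 × 1.44 = 0.4055 × 1.44 = 0.584, whose square is 0.341, so n = 7.849 / [0.341 × p(1−p)]. This gives 93 at p = 0.50, 144 at 0.80, 153 at 0.815 and 156 at 0.82. It equals 154 only at p near 0.817 (or 0.183). The plan states no suppression rate, so 154 is matched but not independently reproduced. The formula treats CTRA as one variable with one SD and the rows as independent.

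**Step 2. Simulation of the blend.** 55 men × 4 visits = 220 rows; CTRA SD 1.44; random-intercept logistic model; 400 runs per scenario (Monte Carlo error at most about 2.5 points). Not in the documents, hence assumed: CTRA intraclass correlation (ICC) 0.3, 0.5 and 0.7; 80% suppressed; random-intercept SD 1; visits at days 0, 35, 63 and 91; no covariates or dropout. The true within-man OR is 1.0. Percentages are the share of trials significant at 5%.

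| Between-man OR | ICC | Undivided CTRA: OR | Undivided CTRA | CTRA main effect beside interaction | Interaction | Within-man term after split |
|---|---|---|---|---|---|---|
| 1.5 | 0.3 | 1.09 | 10% | 7% | 4% | 6% |
| 1.5 | 0.5 | 1.18 | 18% | 10% | 4% | 6% |
| 1.5 | 0.7 | 1.28 | 34% | 17% | 5% | 5% |
| 2.0 | 0.3 | 1.17 | 19% | 9% | 4% | 6% |
| 2.0 | 0.5 | 1.31 | 41% | 20% | 5% | 7% |
| 2.0 | 0.7 | 1.51 | 73% | 40% | 6% | 6% |

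The implied weight on the between-man effect is ln(undivided OR) / ln(1.5): 0.086/0.405 = 0.21, 0.166/0.405 = 0.41 and 0.247/0.405 = 0.61 at the three ICCs. As a check, take opposite effects (between 1.5, within 0.67). The weights predict ORs of exp[(2w − 1) × 0.405] = 0.79, 0.93 and 1.09; the simulation gave 0.80, 0.92 and 1.09. The last points the wrong way for a change question.

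**Step 3. Does the interaction help?** With a true within-man OR of 1.5 (between-man OR 1.0 or 1.5), the interaction is significant in only 3% to 6% of trials, because it tests drift of the slope with days. The main effect beside it is the slope at time zero and stays blended: its ORs in the no-within-effect scenarios are 1.09 to 1.53. It rejects less often than the term fitted alone only because it is less precise.

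**Step 4. Less favourable settings.** A second simulation used random-intercept SD 2, 80% of rows, 18% unsuppressed, 13 noise covariates and 250 runs. With between-man OR 1.5 and no within-man effect, undivided CTRA was significant in 6%, 12% and 22% at ICC 0.3, 0.5 and 0.7. OR 2.0 with ICC 0.7 gave about 37%. With no CTRA effect at all that model rejects in 7%, so the lowest of these values is no inflation.

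**Step 5. Precision of the within-man term.** In the Step 2 setting with a true within-man OR of 1.5, the split term recovers 1.50 to 1.52. Its power on 220 rows is about 58%, 47% and 30% at ICC 0.3, 0.5 and 0.7. If 20% of rows are lost at random, multiplying (1.96 + z_power) by √(176/220) = 0.894 gives roughly 49%, 39% and 25%. Scaling 154 by 1/(1 − ICC) gives 220, 308 and 514 rows. That scaling is optimistic: at ICC 0.3 it promises 80% power on 220 rows, where the simulation gives 58%.

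**The case against.** **Other analyses bear on 3.1.** A reader might infer that the whole plan cannot answer 3.1. The documents do not support that. Section 3.1 names viral load, not suppression; 15.6 adds the dynamic panel model, and 15.7 mentions viral load as a continuous outcome. The panel model may address within-man links if it carries person-specific effects, which the plan does not say. It looks at viral load at later visits, so it does not repair the same-visit suppression model.

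**Not every rejection is an error.** In the simulations a real between-man association exists. For the synopsis wording, and for a plan that recruits a comparison group, finding it is correct. This stands. The fault is only in reading it as change.

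**If the two effects are equal, the undivided term is right and stronger.** With both ORs at 1.5 and no interaction, it gives an OR of 1.50 to 1.51 and 74% to 80% power. That is also true, but the plan does not state or test equality.

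**Two further inferences go beyond the text.** One is that CTRA is centred on the grand mean; the power text says only that it is mean-centred. Grand-mean centering would leave the blend unchanged; centering on each man's mean would not. The other is that suppression barely changes within a man, so that nearly all information lies between men. No passage says so, and the implied weights of 0.21 to 0.61 show that it depends on the ICC.

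**A later SAP is promised** in section 15. That is the place for the correction, but nothing yet commits to it.

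**Conclusion.** The point holds for the CTRA–viral suppression model and no further. Its main effect is a blend, its interaction answers another question, and the plan does not say which of the two carries the conclusion. That the blend exists follows from the model as written. Its size rests on assumptions: CTRA ICC 0.3 to 0.7, between-man OR 1.5 to 2.0, random-intercept SD 1 to 2, and about 80% suppressed. Across these, with no within-man effect, undivided CTRA fitted without the interaction is significant in about 6% to 73% of trials (7% to 40% beside the interaction in the Step 2 setting), against about 5% for a separate within-man term. No single figure in that range should be quoted as the expected error rate. The correction is worth making because it is cheap and bears on the primary objective.

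**What to change.** In the SAP, before any CTRA–suppression results are seen:

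- Replace CTRA in this model by two terms: the man's mean CTRA over his available visits, and the visit value minus that mean. Add study arm to the covariates.
- Name the within-man coefficient as the answer to 3.1 and the between-man coefficient as the answer to the synopsis wording. With arm included, the latter describes differences among men in the same arm; say so. Make the two statements of the objective agree.
- If the time interaction is kept, describe it as a test of drift in the slope, and state the time point to which the main effects refer.
- State whether the dynamic panel model includes person-specific effects.
- Restate 15.7: the 154 observations and 80% power do not apply to the within-man effect.

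The cost is wording and one derived variable, with no new data. The downside should be stated openly: a wider interval, and within-man power of about 58% to 30% for OR 1.5 on all 220 observations (ICC 0.3 to 0.7), lower at 80% retention. The between-man coefficient is also somewhat attenuated, because a four-visit mean is a noisy measure of a man's usual level. With no within-man effect, a true between-man OR of 1.5 was estimated at 1.30, 1.39 and 1.44 at the three ICCs.

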Primary Analysis Plan	Using a linear mixed effects regression, we will test whether a negative MA urine test is associated with reductions in CTRA contrast scores across four time points—Visits B, 4.2 (Week 4), 8.2 (Week 8), and 12.0 (Week 12 follow-up). We will use a time (days) by MA urine result interaction term to estimate difference in change in CTRA as a function of MA test result. Using a mixed effects logistic regression, we will test whether CTRA expression is associated with viral suppression (<200c/mL) across three time points— Visits B, 4.2 (Week 4), 8.2 (Week 8), and 12.0 (Week 12 follow-up). We will include a time (days) by CTRA expression interaction term to test this association longitudinally.
Rationale for Number of Subjects	Power analysis for this pilot study indicates that a minimum of 135 person-observations will be sufficient to test whether MA use or the psychosocial Short Inventory of Problems (SIP-R) are associated with CTRA expression, assuming a medium effect size of 0.15 and power level of .80. Additionally, a logistic model testing whether CTRA is associated with viral suppression would require a minimum of 154 person-observations, assuming a power level of .80, a CTRA standard deviation of 1.44, mean centering of CTRA, and an odds ratio of 1.5. When modeling viral load as a continuous outcome, 135 person-observations is the minimum to test whether CTRA is associated with viral load (c/mL), assuming a medium effect size of 0.15 and power level of .80. These analyses will include 55 participants over four measurements of CTRA, for a total of 220 person-observations (176 person-observations at 80% retention), which is sufficient for these thresholds.

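### The suppression model says three time points but names four visits, and the 220/176 row count is applied to every analysis although the lagged viral-load model has only three outcome waves (165 rows, or 132 at 80% retention, against a stated minimum of 135)

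*Combined protocol and SAP*

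**What the plan says.** **Time points.** Section 15.6 specifies a mixed effects logistic regression of viral suppression on CTRA "across three time points—Visits B, 4.2, 8.2, and 12.0". The synopsis (Primary Analysis Plan) has the same mismatch: "across three time points— Visits B, 4.2 (Week 4), 8.2 (Week 8), and 12.0 (Week 12 follow-up". In both places the companion model of urine result and CTRA gives its count as four for the same four visits.

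**Lagged model.** Section 15.6 adds a dynamic panel model, fitted by maximum likelihood, to "test whether CTRA is associated with viral load at subsequent observations" while allowing CTRA to depend on earlier viral load. No other model in 15.6 treats viral load as anything but suppressed or not suppressed.

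**Row counts.** Section 15.7, repeated in the synopsis, sets two minima that matter here. For suppression, "a logistic model testing whether CTRA is associated with viral suppression would require a minimum of 154 person-observations". For viral load itself, "When modeling viral load as a continuous outcome, 135 person-observations is the minimum". It then credits the analyses together with "55 participants over four measurements of CTRA, for a total of 220 person-observations (176 person-observations at 80% retention" and calls this enough for all the thresholds.

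**The concern.** The first problem is that the row set of a powered model is stated in two incompatible ways within one phrase. An analyst should not have to decide which half to follow.

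The second is that a sufficiency claim built on four waves does not carry over to a model that relates CTRA at one visit to viral load at a later one. Baseline viral load has no earlier CTRA measurement, so four visits supply three outcome waves. As written, the plan shows a margin of 176 - 135 = 41 rows for continuous viral load. If the 135 is meant for the lagged model, the lost wave removes that margin.

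The relation between CTRA and viral load is part of the primary objective (section 3.1), so the stated power should match the model that will be fitted.

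**Working it through.** **Inputs from the documents**
- 55 participants, four CTRA measurements, 80% retention (section 15.7).
- Minima of 154 rows (logistic suppression model) and 135 rows (continuous viral load) (section 15.7).
- Effect size 0.15 and power 0.80 for the 135. Alpha, the test and the number of predictors are not given.
- Viral load at Visits B, 4.2, 8.2 and 12.0 (section 9.2.2), PBMCs at the same four (section 9.3.1), and both in Table 3.

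**Step 1: reproduce the plan's figures.** 55 x 4 = 220, and 220 x 0.80 = 176. Both are exact. The 176 applies a flat 80% to all four waves.

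**Step 2: suppression model.** Both measures exist at all four listed visits, so the same-visit model has 176 rows at 80% retention. 176 exceeds 154, and the minimum holds down to 154/220 = 70% retention. Correcting the count to four therefore settles this part without loss.

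**Step 3: lagged viral-load model.** The outcome waves are 4.2, 8.2 and 12.0.
- Full data: 55 x 3 = 165.
- Flat 80%, the plan's own convention: 165 x 0.80 = 132.
- Shortfall: 135 - 132 = 3 rows, and 3/135 = 2.2%.
- Retention needed for 135 rows: 135/165 = 81.8%.

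**Step 4: a different retention pattern.** Suppose 80% is reached only at Week 12, with linear loss from Baseline. Then the three outcome waves give 55 x (0.933 + 0.867 + 0.80) = 143, which is above 135. Under that pattern four waves would give 55 x (1 + 0.933 + 0.867 + 0.80) = 198, not the plan's 176, so it is not the pattern section 15.7 used.

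**Step 5: size in power terms.** Assume that 0.15 is Cohen's f², that the test is the overall F test, and that alpha is 0.05. Power is P(F > critical value), with F noncentral on u and N - u - 1 degrees of freedom and noncentrality 0.15 x N. With u = 14 predictors the smallest N giving 0.80 is exactly 135. The same test then gives:

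| Rows | Basis | Power |
|---|---|---|
| 135 | stated minimum | 0.80 |
| 132 | three waves, flat 80% | 0.79 |
| 143 | three waves, 80% reached at Week 12 | 0.83 |
| 165 | three waves, full data | 0.90 |
| 176 | four waves, flat 80% | 0.92 |

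The 14 predictors were found by solving for 135 and do not appear in the plan. Six predictors at alpha 0.01 also give 135, whereas a one-degree-of-freedom test at alpha 0.05 would need only 55. This calculation treats rows as independent; section 15.7 states no allowance for correlation within participants either.

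**The case against.** The strongest reply is that nothing has been miscalculated and little is at stake. 220 and 176 are correct products. Section 15.7 never mentions a lag when it sets the 135, and it uses the same figure and effect size for the same-visit model of MA use and CTRA. Section 9.2.2 defines viral load in both continuous and dichotomous form, and the primary objective asks whether changes coincide, so a same-visit continuous model may have been intended. On that reading 176 rows exceed 135. Even on the lagged reading the gap is 3 rows, about one point of power, in a pilot study.

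Most of this stands as to size. It does not remove the inconsistency. If a same-visit continuous model is meant, 15.6 does not describe one. If the lagged model is meant, the row count is wrong for it. Either way 15.6 and 15.7 need to be reconciled.

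Three stronger readings are tempting, and the documents do not support them.
- *The suppression model falls short, with 132 rows against 154.* This requires the word three to be right and the list of four visits to be wrong. No text drops Baseline or any other visit, and both measures are taken at all four. The 154 belongs to this same-visit model, so the lag does not bear on it.
- *The lagged model can have at most 132 rows.* 132 depends on a flat 80% at each outcome wave. Step 4 shows a pattern that gives 143, and section 12.4 replaces participants who withdraw before Visit 5.2, which could add rows.
- *Only about 106 rows remain (55 x 3 x 0.80 x 0.80), because both visits of a pair must be present.* This needs visits to be missed independently and incomplete pairs to be deleted. Under dropout, a participant seen at the later visit was also seen at the earlier one. Maximum likelihood estimation need not discard incomplete pairs.

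**Conclusion.** The point holds in a limited form.

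- **Certain from the text:** the count of time points contradicts the list of visits in both the synopsis and 15.6; the same-visit suppression model meets its minimum once the count reads four; and the lagged model has three outcome waves, which the sample-size text does not recognise.
- **Conditional:** the lagged model is marginally short, 132 rows against 135, with power about 0.79 where 176 rows would imply about 0.92. This rests on flat 80% retention, on the 135 being meant for that model, and on a 14-predictor F test at alpha 0.05. The first is the plan's own convention, the second is an inference, and the third is an assumption.

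The design does not fail. A statement of adequate size has been extended to a model for which it was not worked out.

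**What to change.** 1. In the synopsis (Primary Analysis Plan) and section 15.6, change three to four for the suppression model. If three visits were really intended, name them and restate the logistic power.
2. In section 15.7 and the synopsis (Rationale for Number of Subjects), count rows by model: 220 (176 at 80%) for same-visit models and 165 (132 at 80%) for the lagged panel model. Say what pattern of retention the 80% describes.
3. Limit the sufficiency statement to the same-visit models.
4. State whether the 135 applies to the lagged model or to a same-visit model of continuous viral load. If the latter, add that model to 15.6.
5. Restate power or the detectable effect for the lagged model, giving its alpha and number of predictors.

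The cost is wording in two sections and the synopsis, plus one slightly less favourable figure. No participants, visits or assays change, and the detailed SAP promised at the start of section 15 can carry the restated figures.
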